Title: The safety and effectiveness of clinical performance of Breath-O correct orthokeratology lenses

(NCT03616600)

Date: 10th March, 2019

Title: The safety and effectiveness of clinical performance of Breath-O correct orthokeratology lenses

Methods:

Sample size: 15 subjects for each group were recruited

Groups: Treatment group – prescription of Breath-O Correct lens Control group – non-contact lens wearer

Inclusive criteria:

Age: 18 to 30 years

Refractive error: Spherical: normally -1.00D to -4.00D (maximum up to -5.00D); Cylindrical: normally \leq half of Sph (against-the-rule Astig.: \leq -0.75D) (maximum up to \leq -1.50D)

Best corrected Visual acuity: monocular ETDRS 0.0 or better

Ocular health: No ocular abnormality, no contra-indications for overnight orthokeratology lens wear, no refractive surgery

General health: No systemic diseases

Requirement: No history of orthokeratology lenses wearing. Agree to participate in this study and willing to wear the orthokeratology lenses overnight in accordance with the instructions given and to come back for follow up within the study period

Parameters to be assessed:

Effectiveness: Objective and subjective refractive error, central corneal thickness, high contrast visual acuity, low contrast visual acuity, corneal topography

Safety: Corneal epithelium and endothelium health, corneal resistance factor and corneal hysteresis, tears quality.

Subjective evaluation: OSDI Questionnaire

Analysis: Categorical variables were presented as number or percentage, while continuous variables were presented as mean and standard deviation. Data from both eyes of each subject were analyzed for follow-up visits (within subjects) and for group comparison (between groups). RM-ANOVA, 2-way ANOVA and Friedman test were used for comparison. The significance level is set at p<0.05.

Protocol:

- All the subjects had a baseline eye examination with all the above tests. A written consent was obtained from each eligible subject before randomly allocating into treatment group (fitting of the contact lenses) or control group (no fitting of contact lens)
- A pair of Breath-O Correct lenses were prescribed for each eligible subject of the treatment group with full wearing instructions of orthokeratology
- After successful prescription of the lenses, the subjects of the treatment group came back for regular visits listed in Figure 1
- For the subjects of the control group, all had the eye examination same as those received by treatment group at the time point of baseline, 1st month and 3rd month.

[figure not shown]

Figure 1. Schedule of visits

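### The planned safety analysis has no interval estimates, no stated rule for fellow eyes and, if any safety measure is graded or yes/no, no suitable between-group test

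*Combined protocol and SAP*

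**What the plan says.** The title, "The safety and effectiveness of clinical performance of Breath-O correct orthokeratology lenses", puts safety beside effectiveness. Under Parameters to be assessed, the safety list is "Safety: Corneal epithelium and endothelium health, corneal resistance factor and corneal hysteresis, tears quality". It gives no measurement scale, event definition, grade threshold or acceptable limit.

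The Analysis paragraph covers safety and effectiveness together in four sentences:

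- Summaries: "Categorical variables were presented as number or percentage, while continuous variables were presented as mean and standard deviation".
- Data used: "Data from both eyes of each subject were analyzed for follow-up visits (within subjects) and for group comparison (between groups".
- Tests: "RM-ANOVA, 2-way ANOVA and Friedman test were used for comparison". They are not matched to outcomes.
- Level: "The significance level is set at p<0.05".

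On size, the document says only "Sample size: 15 subjects for each group were recruited". Allocation is random. Under Protocol, "the subjects of the treatment group came back for regular visits listed in Figure 1" (the figure is not available to us). Controls are examined at baseline, month 1 and month 3. The visits known to be common to both groups are therefore baseline and those two months.

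**The concern.** A safety question asks how large a harm the data still allow. P-values from 15 subjects per group do not answer it, and the plan names no interval that would. A reader could rebuild unadjusted intervals from the reported summaries only if those are per subject. The unit (subject or eye) is not stated, and baseline-adjusted differences cannot be rebuilt from means and SDs.

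Two further gaps bear on the group comparison. First, both eyes enter it with no mention of averaging, eye selection, an eye factor or a subject random effect. If fellow eyes were counted as separate observations, intervals would be too narrow and false positives too frequent. Second, Friedman is the only rank-based test named, and it compares repeated measures within blocks. It cannot compare treated subjects with controls. If epithelial, endothelial or tear findings are recorded as grades or as present/absent, the announced group comparison has no suitable test for them.

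**Working it through.** The plan's 15 per group cannot be reproduced, because no power, effect size, SD, event rate or margin is given. The checks below ask what 15 per group can show. From the document: 15 subjects per group, two eyes each, two-sided 5% level assumed (sidedness is not stated). Not in the document, hence shown as ranges: the between-eye correlation ρ and the correlation r between baseline and follow-up. All 15 subjects per group are taken as evaluable.

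**Yes/no findings (illustrative, since no event is defined).** Exact two-sided 95% limits:

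- 0 of 15 treated subjects: upper limit 1 − 0.025^(1/15) = 21.8%.
- 0 of 30 eyes, wrongly taken as independent: 1 − 0.025^(1/30) = 11.6%.
- 1 of 15 subjects: 0.2% to 31.9% (Clopper-Pearson).

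**Continuous measures, one visit.** The 95% half-width of the group difference is:

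- One value per subject: t(0.975, 28) × √(2/15) = 2.048 × 0.365 = 0.75 SD.
- Mean of two eyes, in eye-level SDs: t(0.975, 28) × √[(2/15)(1+ρ)/2] = 0.65, 0.69 and 0.73 for ρ = 0.5, 0.7 and 0.9.
- 60 eyes taken as independent: t(0.975, 58) × √(2/30) = 2.002 × 0.258 = 0.52 SD. This would be reported where 0.65 to 0.73 is correct.
- Mean of two eyes, adjusted for baseline: t(0.975, 27) × √[(1−r²)(2/15)(1+ρ)/2], ignoring chance baseline imbalance:

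| r | ρ = 0.5 | ρ = 0.9 |
|---|---|---|
| 0.5 | 0.56 | 0.63 |
| 0.7 | 0.46 | 0.52 |
| 0.8 | 0.39 | 0.44 |
| 0.9 | 0.28 | 0.32 |

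**False-positive rate if eyes were treated as independent.** Simulating 200,000 normal trials with 15 subjects × 2 eyes per group and a nominal 5% single-visit t-test:

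| ρ | Eye-level test | Subject-mean test |
|---|---|---|
| 0.5 | 11.0% | 4.9% |
| 0.7 | 13.7% | 4.9% |
| 0.9 | 16.3% | 5.0% |

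**What an added Fisher test can do.** Two-sided, 4/15 v 0/15 gives p = 0.100 and 5/15 v 0/15 gives p = 0.042. At least five events are therefore needed against none. Power for a true 20% v 0% is P(X ≥ 5 | 15, 0.2) = 16%. The test's true size with equal rates of 5% to 30% in both groups is below 2%.

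**Multiplicity.** Five safety measures at two common visits make 10 tests. If independent and each of exactly 5% size, the chance of at least one false positive is 1 − 0.95^10 = 40%. It is lower where Fisher is used.

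**The case against.** The strongest reply is that much of the harm is conditional. A reader might infer that the plan counts 60 eyes as independent and so runs at an 11% to 16% error rate. The text does not say so. RM-ANOVA or 2-way ANOVA could carry eye as a within-subject factor, and the simulated t-test is not one of the three named tests. Only the absence of a stated rule is established; the error rates show what that absence could cost.

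A reader might also infer that safety has no between-group test at all. That is wrong as well. A group comparison is announced, and 2-way ANOVA can serve corneal hysteresis, corneal resistance factor and any other continuous measure. Endothelial and tear findings may be continuous too. The gap exists only for measures that are graded or yes/no. The plan provides for categorical variables but does not say whether any safety measure is one.

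It is also fair to say that a short paragraph silent on intervals does not prevent their being reported, and that intervals disclose imprecision without removing it. For proportions the width does come from the sample size. For continuous measures the choice of analysis matters, as the baseline-adjusted half-widths show.

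What stands is that neither an interval nor a fellow-eye rule appears anywhere in the document, and that Friedman cannot compare groups.

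**Conclusion.** The concern holds with limits. Two omissions are certain: no interval estimate and no stated handling of fellow eyes. The third, the lack of a suitable group test, is conditional on a safety measure being graded or yes/no.

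On size, no events in 15 treated subjects would remain compatible with a rate of up to 21.8%, or roughly one in five. The planned outputs would not show this. Treating eyes as independent would nearly halve that limit to 11.6% and would state a 0.52 SD half-width where 0.65 to 0.73 SD is correct. These figures rest on full follow-up, on assumed values of ρ and r, and on an event that the document does not define.

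A reader might infer that the plan intends to read a non-significant result as proof of safety. It does not say that, and the point does not depend on it. The safety statement should be repaired; the trial is not invalidated.

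**What to change.** 1. For corneal hysteresis, corneal resistance factor and other continuous safety measures, report the between-group difference at months 1 and 3 with a 95% CI. Adjust for baseline and take the subject as the unit, using either the mean of the two eyes or a mixed model with a subject random effect.
2. State the scale of each epithelial, endothelial and tear measure. Where it is graded or yes/no, compare groups at subject level at months 1 and 3 by Wilcoxon rank-sum or Fisher exact test, and keep Friedman for within-group description. For yes/no findings, give subject-level incidence with exact 95% CIs and a 95% CI for the between-group risk difference (for example Newcombe or exact unconditional). List findings from any treatment-only visits separately.
3. Label as post hoc any finding definition, grade threshold, worse-eye rule or main time point chosen after the data were seen. The document's past tense makes this a live issue. Treat the safety p-values as exploratory. If no acceptable limit was fixed beforehand, report the intervals without a safe/unsafe verdict.

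The cost is slightly more analysis and a less favourable safety statement; no subjects, visits or procedures are added. Because Fisher is weak at this size, the intervals should carry the conclusion.

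### The stated safety outcome is a set of examination readings, so lens-related events, stopped wear and failed fittings may go uncounted

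*Combined protocol and SAP*

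**What the plan says.** Safety comes first in the trial's title. Under Parameters to be assessed it is given one line: "Safety: Corneal epithelium and endothelium health, corneal resistance factor and corneal hysteresis, tears quality". A separate line, "Subjective evaluation: OSDI Questionnaire", adds a symptom questionnaire, which is not listed as a safety measure.

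The Analysis paragraph summarises categorical data as counts or percentages and continuous data by mean and SD, uses both eyes of each subject, and states that "RM-ANOVA, 2-way ANOVA and Friedman test were used for comparison". It gives no analysis population and no rule for missing visits.

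On follow-up, the Protocol section says: "After successful prescription of the lenses, the subjects of the treatment group came back for regular visits listed in Figure 1". Controls "all had the eye examination same as those received by treatment group at the time point of baseline, 1st month and 3rd month". The sample size entry says "15 subjects for each group were recruited". Willingness to return for follow-up is an entry requirement. It is not a rule for visits that are missed or for subjects who stop wearing the lens.

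**The concern.** A trial of an overnight lens can lose safety information by three routes that the stated outcome does not close.

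- An ocular event may begin and resolve between two examinations. The next reading can then be normal, whichever test is used and even if nobody drops out.
- A subject may leave because of the lens and give no later readings.
- A subject may be randomised to the lens but not fitted successfully. Return visits are described only for those with a successful prescription, so such a subject has no stated place in the safety result.

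At stake is whether the safety conclusion describes everyone allocated to the lens or mainly those who tolerated it. With 15 subjects in the arm, a single person can change the answer.

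**Working it through.** **Inputs.** From the document: 15 subjects per group; visits common to both groups at baseline, month 1 and month 3; the three named tests; a 0.05 significance level. Assumed, because the document gives no event or dropout figures: 1, 2 or 3 treated subjects have a lens-related event and leave, and no event is recorded among those who remain.

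**The plan's own figure.** The 15 per group comes with no event rate, effect size, SD, power or dropout allowance, so it cannot be reproduced. It is taken as given.

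**Step 1: what each named method does with a missing visit.** RM-ANOVA and Friedman in standard form need a value at every visit. A subject who misses one is excluded, and both eyes go. A 2-way ANOVA and per-visit percentages can keep readings from visits that were attended. Loss from the safety tests is therefore possible but not certain. An event that resolves between visits is missed under all of these methods, because no reading captures it.

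**Step 2: effect on the observed rate.** With x affected subjects, the rate among all randomised is x/15. Among those remaining it is 0/(15 − x). Limits are exact (Clopper-Pearson) 95% limits; for zero events the two-sided upper limit is 1 − 0.025^(1/n).

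| x (assumed) | All randomised | 95% CI | Remaining only | Upper 95% limit |
|---|---|---|---|---|
| 1 | 1/15 = 6.7% | 0.2% to 31.9% | 0/14 = 0% | 23.2% |
| 2 | 2/15 = 13.3% | 1.7% to 40.5% | 0/13 = 0% | 24.7% |
| 3 | 3/15 = 20.0% | 4.3% to 48.1% | 0/12 = 0% | 26.5% |

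Even with nobody lost, 0/15 has an upper limit of 1 − 0.025^(1/15) = 21.8%.

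**Step 3: is an affected subject plausible?** The chance of at least one event among 15 is 1 − (1 − p)^15. At assumed true rates p of 2%, 5%, 10% and 20% it is 26%, 54%, 79% and 96%.

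**Step 4: what a between-arm comparison could show.** Take 2/15 against 0/15. The probability that both events fall in the treated arm is C(15,2)/C(30,2) = 105/435 = 0.241, so the two-sided Fisher p-value is 2 × 0.241 = 0.48. A count at this sample size is descriptive only.

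**The case against.** **Complete-case analysis.** A reader might infer that the plan prescribes a complete-case safety analysis, so that anyone who stops is certain to disappear from it. The document does not say so. The inference comes from the names of two tests, while 2-way ANOVA and the categorical summaries can retain readings made before the subject left. An abnormality seen at an attended visit could still be reported. This part of the objection stands, and the point is limited to what may be lost.

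**Visit spacing.** Figure 1, the visit schedule, is not visible in the text reviewed, and the separate wording for the two groups suggests that treated subjects may have extra visits. Closer visits would make it less likely that an event resolves unseen. They would not create an event count or a rule for subjects who leave.

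**Other measures.** The safety list does not forbid reporting events, and the OSDI gives a subjective measure in both arms. Both are true, but a questionnaire completed at visits is not a record of events or of stopped wear.

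**Direction.** A reader might infer that all missing data here favour the lens. The document does not support that, because controls can miss visits too. Only lens-related stopping is confined to one arm, since controls wear no contact lenses.

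**Remedy.** A composite comparing the arms on events plus interrupted wear would be tempting. One component cannot occur in controls, so such a comparison would be tilted against the lens. This objection also stands, and the fix keeps the two apart.

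**Conclusion.** The point holds in a limited form. The stated safety outcome does not count ocular adverse events, unscheduled eye visits, or paused, stopped or unsuccessful lens wear. Applied as written, it could give clean readings while lens-related events and stops go unreported.

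The route through events that resolve between visits does not depend on the choice of test. The route through dropout depends on which of the named tests is used and how missing visits are handled.

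The size cannot be derived from the document, which reports no events or dropout and names no grading scale from which a shift in mean readings could be calculated. The contrast of 6.7% to 20.0% with 0% illustrates how sensitive an arm of 15 is. It is not an estimate of bias in this trial.

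**What to change.** 1. Add to the safety results, for all randomised subjects (15 per arm, including any whose fitting was unsuccessful), the number with at least one ocular adverse event or unscheduled eye visit. Collect it with the same questions in both arms at the existing 1- and 3-month visits. Compare the arms descriptively with exact confidence intervals.
2. Report interruption or discontinuation of lens wear, with reasons, separately and for the treatment arm only. Do not combine it with events in a between-arm outcome.
3. Continue the 1- and 3-month examinations for subjects who stop lens wear, where they agree. Include any examination made at stopping in the safety summary, and account for every randomised subject.
4. Much of the document is in the past tense. If follow-up is already complete, compile the events, stops, reasons and last examinations from existing records.

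The cost is a few questions and one table, and the safety result may look less favourable. Two limits remain: recall between months 1 and 3 spans up to two months, and a subject who withdraws and does not return can be accounted for only from what was recorded before leaving.

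### Both eyes of each randomised subject are analysed with no rule for their correlation; if eyes were counted as independent, type I error is about 6% at an assumed correlation of 0.1 and about 8.5–16% at 0.3–0.9

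*Combined protocol and SAP*

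**What the plan says.** All of this comes from the combined protocol and SAP.

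- **Sample size:** "Sample size: 15 subjects for each group were recruited". No effect size, standard deviation or power is given.
- **Protocol, allocation:** "A written consent was obtained from each eligible subject before randomly allocating into treatment group". The subject is the unit of randomisation.
- **Protocol, lens prescription:** "A pair of Breath-O Correct lenses were prescribed for each eligible subject of the treatment group". Both eyes of a treated subject receive the lens.
- **Protocol, control visits:** controls "all had the eye examination same as those received by treatment group at the time point of baseline, 1st month and 3rd month". The two groups therefore share three visits.
- **Analysis:** "Data from both eyes of each subject were analyzed for follow-up visits (within subjects) and for group comparison (between groups"; then "RM-ANOVA, 2-way ANOVA and Friedman test were used for comparison"; then "The significance level is set at p<0.05".

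Apart from descriptive summaries, that is the whole analysis plan. It does not mention eye as a factor, averaging, choice of one eye, a subject effect or a clustering adjustment.

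**The concern.** Two eyes of one person are not two independent observations, and here they are always in the same group. If each eye counts as a separate unit, the information in 15 subjects is treated as if it came from 30. Standard errors for group comparisons are then too small, and p falls below 0.05 too often when nothing differs.

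Two of the three named tests invite this. A standard 2-way ANOVA has no subject term, and the Friedman test takes one value per block per visit. Adding eye as an ordinary factor to the 2-way ANOVA does not help, because the error term is still between eyes. RM-ANOVA avoids the problem if eye is a repeated factor within subject, but the plan does not say that it is.

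The measures at stake are those taken per eye: refraction, acuity, corneal thickness, topography, and the eye-level safety measures ("Corneal epithelium and endothelium health, corneal resistance factor and corneal hysteresis, tears quality"). With 15 subjects per group, the choice between 15 and 30 units can decide whether a result is significant. The open rule also lets the unit be chosen after the results are seen. OSDI, apparently one score per subject, is not affected.

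**Working it through.** **Inputs from the document.** 15 subjects per group; subject randomised; both eyes analysed; alpha 0.05; three shared visits (baseline, month 1, month 3). The sample size has no stated basis, so there is no calculation to reproduce.

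**Assumptions.** Two-sided tests; normal data; no true effect; eyes counted as independent. The inter-eye correlation ρ is not given and is varied from 0.1 to 0.9.

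**Group comparison, formula.** With two eyes per subject, the variance of a group mean is σ²(1+ρ)/30. An analysis of 30 independent eyes uses σ²/30. So:

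- effective eyes per group = 30/(1+ρ)
- understatement of the standard error = 1 − 1/√(1+ρ)
- type I error = 2·[1 − Φ(1.96/√(1+ρ))]

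At ρ = 0 the last formula returns 5.0%, as it should. At ρ = 0.5, 1.96/√1.5 = 1.600, which gives 11.0%.

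| ρ | 0.1 | 0.3 | 0.5 | 0.7 | 0.9 |
|---|---|---|---|---|---|
| Effective eyes per group | 27.3 | 23.1 | 20.0 | 17.6 | 15.8 |
| SE understated by (%) | 4.7 | 12.3 | 18.4 | 23.3 | 27.5 |
| Type I error, formula (%) | 6.2 | 8.6 | 11.0 | 13.3 | 15.5 |
| Pooled eyes, 30 v 30, simulated, 60,000 replicates (%) | 6.1 | 8.5 | 11.2 | 13.7 | 16.1 |
| Same, separate run of 400,000 (%) | 6.2 | 8.7 | 11.2 | 13.8 | 16.3 |
| 2-way ANOVA, group × eye, eye as ordinary factor, 60,000 (%) | 6.0 | 8.4 | 10.9 | 13.3 | 15.5 |
| Two-eye means, 15 v 15, 60,000 (%) | 5.0 | 4.9 | 5.0 | 5.0 | 4.9 |

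**Tests involving visits.** Here ρ is the correlation between fellow eyes of the deviations from visit to visit. It may be lower than the correlation of the levels, because deviations include eye-specific measurement noise. Three visits, 40,000 replicates:

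| ρ of visit deviations | 0.1 | 0.3 | 0.5 | 0.7 | 0.9 |
|---|---|---|---|---|---|
| Group × visit, eyes as units (%) | 6.6 | 10.1 | 14.0 | 18.2 | 21.9 |
| Group × visit, two-eye means (%) | 5.0 | 5.0 | 5.2 | 5.1 | 5.2 |
| Friedman, 30 eye-blocks (%) | 6.7 | 9.2 | 12.2 | 15.8 | 19.7 |
| Friedman, 15 two-eye-mean blocks (%) | 4.9 | 4.6 | 4.7 | 4.8 | 4.8 |

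The Friedman test on 30 eye-blocks gives 5.4% at ρ = 0, so almost all of its excess comes from the correlation. The treatment-group schedule is in a figure that is not shown, so a within-treatment Friedman test may have more than three visits.

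**Check of a mixed model as an alternative remedy.** The plan does not propose one. The check covers 4,000 replicates of the group × visit test, with assumed variances of 1 (subject), 0.3 (eye) and 1 (visit deviation). Random intercepts for subject and eye alone leave the error at 6.4–22.3% over the same range of ρ. Adding a subject-by-visit effect brings it to 4.6–5.9%, against 4.8–5.9% for two-eye means on the same datasets. Monte Carlo error is about 0.35 points at 5%.

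**The case against.** The best defence is that the document shows an omission and not an error. It never says that eyes were independent units. RM-ANOVA is named, the sentence uses a within-subjects label, and the wording is compatible with eye as a repeated factor, with averaging, or with separate analyses of right and left eyes. The factors of the 2-way ANOVA are not named. The Friedman test is not tied to any endpoint and might have been used only for OSDI or for graded findings, whereas the simulation uses continuous data without ties. The correlation is assumed, and the assumed range runs from a trivial to a large effect. For safety measures, inflation would over-declare harms and not hide them.

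Most of this stands as a limit on the size of the problem. The percentages are conditional, and the upper ends, especially 19.7–22.3% for tests involving visits, should not be read as expected values. It does not remove the gap. The within-subjects label describes the visit comparison; the group comparison is listed separately, and nothing is said there about pairing of eyes. A reader cannot tell from the plan which p-values are valid.

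It is also right that two-eye means are not the only valid method. With complete, balanced data, eye as a repeated factor within subject is equivalent. The simple mean also needs a definition for cylinder and a rule for a subject with one usable eye.

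**Conclusion.** The concern holds. That the plan gives no rule for the two eyes is clear from the text. That inflation occurred is not known; it depends on how the tests were run.

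If eyes were counted as independent, a nominal 5% group comparison has a type I error of about 6% at ρ = 0.1 and about 8.5–16% at ρ = 0.3–0.9, with the standard error understated by about 5% and 12–27% respectively. Tests involving visits could be affected more, reaching about 20–22% if visit deviations correlate at 0.9 between eyes. These figures assume two-sided tests, normal data and the stated range of ρ. Because the gap covers every eye-level effectiveness and safety measure, it should be closed before any p-value is relied on.

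**What to change.** 1. State that the subject is the unit of analysis for all eye-level measures. Analyse the mean of the two eyes at each visit, also in the Friedman test, with N = 15 v 15.
2. Accept equivalent methods if specified in full. One is RM-ANOVA with eye as a repeated factor within subject, for complete data. Another is a mixed model with subject, eye-within-subject and subject-by-visit effects (or an equivalent covariance between fellow eyes at the same visit) and small-sample degrees of freedom. Random intercepts alone are not enough for visit or group × visit tests.
3. Define the components of refraction and topography that are averaged, and the rule for a subject with one usable eye.
4. For graded safety findings, fix one per-subject summary before the re-run. As data are already collected, report it as set after collection.
5. Separately, if right and left eyes are tested separately, name one eye as primary or control multiplicity. Each such test holds about 5%, but the chance that at least one eye is significant is 7.1–9.6% over the same range of ρ.

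The cost is SAP wording and a re-run, with no new data. If eyes had been pooled, p-values will become less favourable. If eye was already a repeated factor within subject, only the wording changes.

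### None of the three listed tests is assigned to the group comparison and no baseline covariate is named; adjusting for baseline would use data already collected, with a gain that depends on an unstated correlation

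*Combined protocol and SAP*

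**What the plan says.** The Methods section of the combined protocol and SAP separates two kinds of comparison: "Data from both eyes of each subject were analyzed for follow-up visits (within subjects) and for group comparison (between groups". The next sentence of the Analysis paragraph lists the methods for both together: "RM-ANOVA, 2-way ANOVA and Friedman test were used for comparison". It does not link any test to either kind of comparison, state the ANOVA factors, or name a covariate. No covariate appears elsewhere in the document.

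The data needed for adjustment exist:

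- The first Protocol bullet states that "All the subjects had a baseline eye examination with all the above tests".
- The same bullet makes allocation random: "A written consent was obtained from each eligible subject before randomly allocating into treatment group".
- The control-group bullet has controls examined "at the time point of baseline, 1st month and 3rd month", with the same examination as the treatment group.
- The sample size is small: "15 subjects for each group were recruited".

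**The concern.** A reader cannot tell how the groups are compared. Baseline could enter as a covariate, as one level of a visit factor, or not at all. The Friedman test in its standard form ranks within subjects, so one of the two ANOVAs presumably makes the group comparison. That is an inference, because the text makes no assignment.

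What is at stake is precision. With 15 per group, an unadjusted two-group comparison at two-sided 0.05 has 80% power only for a difference of about 1.06 SD. Where a measure correlates with its own baseline, adjustment narrows the interval using data already in hand. This may matter most for the safety measures, such as corneal hysteresis and endothelial health, where a wide interval reassures little.

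**Working it through.** The plan gives no effect size, SD, power or dropout, so there is no figure of its own to reproduce.

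**Inputs from the document:** 15 subjects per group; significance level 0.05 (sidedness not stated, two-sided assumed); baseline, month 1 and month 3 shared by both groups.

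**Assumptions not in the document:** one value per subject per visit, no dropout, unit SD, equal correlation r between visits, and a constant 0.8 SD effect at months 1 and 3. r is shown over a range.

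**Variance of the month-3 group difference, relative to the unadjusted comparison**

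- Unadjusted: 1.
- Change score: 2(1 − r).
- ANCOVA: (1 − r²)(1 + 1/(2n − 4)). With n = 15 the last factor is 1 + 1/26 = 1.038.

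For ANCOVA:

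- r = 0: 1 × 1.038 = 1.04
- r = 0.2: 0.96 × 1.038 = 1.00
- r = 0.5: 0.75 × 1.038 = 0.78
- r = 0.7: 0.51 × 1.038 = 0.53

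Break-even is where 1 − r² = 26/27, so |r| = √(1/27) = 0.19. Allowing for the lost degree of freedom, it is 0.20.

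**95% CI half-width.** Unadjusted: t(28) × √(2/15) = 2.048 × 0.365 = 0.75 SD. ANCOVA: t(27) × √(2/15 × relative variance), which gives 0.76, 0.75, 0.73, 0.66 and 0.55 SD at r = 0, 0.2, 0.3, 0.5 and 0.7.

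**Simulated power (%) for the assumed 0.8 SD effect** (40,000 replicates)

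| Analysis | r=0 | 0.2 | 0.3 | 0.5 | 0.7 | 0.9 |
|---|---|---|---|---|---|---|
| Unadjusted month 3 | 56.0 | 56.3 | 56.3 | 56.2 | 56.2 | 56.0 |
| ANCOVA month 3 | 54.6 | 56.5 | 58.4 | 66.9 | 82.5 | 99.6 |
| Change score month 3 | 32.2 | 38.5 | 42.9 | 56.1 | 77.7 | 99.7 |
| Group × visit interaction | 32.3 | 39.2 | 44.5 | 59.1 | 81.8 | 99.9 |

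All four reject 4.8 to 5.3% of the time under the null. At r = 0.8 the interaction is about 1 point ahead of ANCOVA (94.7 v 93.4%).

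**If treated eyes lose their baseline correlation.** This is possible for refraction or topography, which the lens is meant to change. Suppose the correlation is r in controls and 0 in the treated group, with equal SDs. The common slope is then about r/2, and the average residual variance is 1 − r²/4. Break-even moves to r/2 = 0.19, so r is about 0.4 in controls. Simulated power, ANCOVA against unadjusted, by control r:

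- 0.3: 55.6 v 56.5%
- 0.4: 57.1 v 57.1%
- 0.5: 57.2 v 56.0%
- 0.7: 60.8 v 56.6%
- 0.9: 64.9 v 56.3%

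**Two eyes entered as independent rows** (20,000 replicates). At an assumed inter-eye correlation of 0.5 / 0.8, null rejection in the month-3 group comparison is about 11 / 15% unadjusted and about 11 / 15% with ANCOVA. Averaging the eyes restores about 5% in both.

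**The case against.** The strongest reply is that the gain is measured against an analysis the plan may not use. An unadjusted month-3 comparison is not among the listed tests. A group by visit interaction is a natural reading of the two ANOVAs, and it already uses baseline. This stands: against the interaction ANCOVA gains about 8 points at r = 0.5, under 1 point at r = 0.7, and is slightly behind at 0.8 and 0.9. The interaction test alone, however, does not give a month-3 difference with an interval.

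The 0.8 SD effect is also assumed. At an assumed 2 SD, unadjusted power is already 99.9%, so adjustment could not improve it. Effects on refraction or topography might be that large; the documents do not say.

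A reader might infer four stronger things, none of which the documents support:

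- *That adjustment will usually raise power here.* This needs the correlation for each outcome, and none is given.
- *That the planned analysis dilutes the effect.* A group main effect with baseline as one of three visit levels would shrink a constant 0.80 SD effect to 0.80 × 2/3 = 0.53 SD. The plan does not say that this model was used, so the figure carries no weight.
- *That an unadjusted comparison is biased.* Allocation was random, so it is not.
- *That adjustment supplies the confidence interval or deals with the paired eyes.* An unadjusted comparison can also carry an interval, and eye-level ANCOVA has the same inflated error rate as the unadjusted analysis.

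**Conclusion.** The point holds as a gap in specification and a conditional missed gain in efficiency, not as an error. The test for the group comparison is unassigned, no baseline covariate is named, and the baseline data were collected. Under the stated assumptions, adjustment lifts power over an unadjusted month-3 comparison by about 11 points at r = 0.5 and 26 points at r = 0.7. It does nothing near r = 0.2 and costs 1 to 2 points at r = 0. The gain is negligible against a group by visit interaction at r of 0.7 or more. If treated eyes lose their baseline correlation, it is nil near r = 0.4 in controls and well below the equal-correlation gain above that. The handling of paired eyes is a separate problem that adjustment neither causes nor cures.

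**What to change.** State which analysis makes the group comparison. For each continuous outcome, use ANCOVA at 3 months with the baseline value of the same measure as covariate. Alternatively, use a mixed model on the month-1 and month-3 values with group, visit, group by visit and baseline. Work on one value per subject per visit (eyes averaged), or model eye within subject with small-sample degrees of freedom. Analyse the OSDI questionnaire at subject level. Report the adjusted 3-month difference with its 95% CI beside the unadjusted one. For refraction and topography, check descriptively whether the baseline slope differs between groups. Keep RM-ANOVA and Friedman for visit comparisons within a group.

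The cost is wording and model fitting, one degree of freedom, and 1 to 2 points of power if baseline is uncorrelated with follow-up. The plan is written in the past tense. If the adjusted analysis is added after the data were seen, it must be labelled as not pre-specified, which lowers its evidential weight.
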